# **Intrapatient Dose Escalation**

When the recommended dose has been determined, patients enrolled in the Rollover Cohort or TN/U Dose Evaluation Cohort of the study who have been on study for at least 8 weeks may have their current dose escalated to the dose level that has been previously determined to be safe in this study, at the discretion of the CTSC.

# 6.2.1.2. Azacitidine

#### **Dose Modifications**

Dose modification or dose delay of azacitidine may not occur for patients in the initial 28-day DLT Assessment Period in the TN/U Dose Evaluation Cohort or for the first cycle for patients in the TN/U Expansion Cohort. Dose modifications described below are in accordance with the azacitidine prescribing information with modifications. While the US prescribing information allows for dose escalation to 100 mg/m^2 after the first 2 cycles, a consistent azacitidine dose of 75 mg/m^2 is planned throughout this study. Azacitidine dose increases are not allowed without prior approval from the Medical Monitor. The azacitidine dose modifications described below are per prescribing information and serve as general recommendations. However, in standard clinical practice, azacitidine label instructions for dose reduction (based on nadir blood counts and bone marrow assessment) are not routinely followed in the clinical setting, and it appears that this part of the label has not been updated since the first approval of azacitidine in 2004. Recommendations from international groups underline the importance of maintaining azacitidine dose intensity in higher-risk MDS patients and AML patients and to avoid dose reductions, if possible (Fenaux 2010; Santini 2014; Wells 2014). Therefore, azacitidine dose modifications will follow the prescribing information below or institutional practice supported by international recommendations.

# Azacitidine Dose Modifications Due to Non-Hematological Toxicity

Renal abnormalities ranging from elevated serum creatinine to renal failure have been reported in rare frequency in patients treated with azacitidine. In addition, renal tubular acidosis, defined as a fall in serum bicarbonate to < 20 mmol/L in association with an alkaline urine and hypokalemia (serum potassium < 3 mmol/L) have been rarely observed. If unexplained reductions in serum bicarbonate (< 20 mmol/L) occur, the azacitidine dose should be reduced by 50% on the next cycle. Similarly, if unexplained elevations in serum creatinine or blood urea nitrogen (BUN) to ≥ 2-fold above baseline values and above the ULN occur, the next cycle should be delayed until values return to normal or baseline and the azacitidine dose should be reduced by 50% on the next treatment cycle. The reduced dose should be maintained during subsequent cycles unless toxicity develops.

# Azacitidine Dose Modifications Due to Hematological Toxicity

Treatment with azacitidine is associated with anemia, neutropenia, and thrombocytopenia. Thus, complete blood counts (CBCs) will be performed as described in the Schedule of Assessments (Section 7.1) and as needed to monitor toxicity. Importantly, these cytopenias are often a result of underlying hematological disease. It is thus critical to distinguish between cytopenias due to azacitidine compared to underlying disease, as to not limit potential treatment benefit. In accordance to this distinction, azacitidine will not be dose-reduced if hematologic cytopenias are observed in the presence of persistent AML; i.e., evidence of:

- > 5% blasts in the bone marrow;
- blasts with Auer rods;
- circulating blasts;
- persistent cytogenetic/molecular abnormality related to AML; or
- positive minimal residual disease.

Hematologic cytopenias in this circumstance are not defined as hematologic toxicities. However, if hematologic cytopenias are observed without evidence of AML disease, this would be defined as hematologic toxicity and azacitidine dose reduced accordingly as below. Guidance for azacitidine dose modifications due to hematologic toxicities are outlined below for 2 patient populations.

Patients without reduced baseline blood counts (i.e., WBC  $\geq$  3.0 × 10 $^{9}$ /L, absolute neutrophil count [ANC]  $\geq$  1.5 × 10 $^{9}$ /L, and platelets  $\geq$  75 × 10 $^{9}$ /L) prior to first treatment.

If hematological toxicity is observed following azacitidine treatment, the next cycle of therapy should be delayed until the platelet count and the ANC have recovered. If recovery is achieved within 14 days, no dose adjustment is necessary. However, if recovery has not been achieved within 14 days, the dose should be reduced according to Table 6-2. Following dose modifications, the cycle duration should return to 28 days. The reduced dose should be maintained during subsequent cycles that are given unless toxicity develops.

Table 6-2. Azacitidine Dose Modification - Patients Without Reduced Baseline Blood Counts

Nadir Counts		% Dose in the Next Cycle If Recovery a Is Not	
ANC (×109/L)	Platelets (×10  /L)	Achieved Within 14 Days	
≤ 1.0	≤ 50.0	50%	
> 1.0	> 50.0	100%	

Abbreviation: ANC = absolute neutrophil count.

Patients with reduced baseline blood counts (i.e., WBC <  $3.0 \times 10^9$ /L or ANC <  $1.5 \times 10^9$ /L or platelets <  $75.0 \times 10^9$ /L) prior to the first treatment

Following azacitidine treatment, if the decrease in WBC or ANC or platelets from that prior to treatment is  $\leq 50$  %, or greater than 50% but with an improvement in any cell line differentiation, the next cycle should not be delayed and no dose adjustment made. If the decrease in WBC or ANC or platelets is greater than 50% from that prior to treatment, with no improvement in cell line differentiation, the next cycle of azacitidine therapy should be delayed until the platelet count and the ANC have recovered. If recovery is achieved within 14 days, no dose adjustment is necessary. However, if

a. Recovery = counts ≥ nadir count + (0.5 × [baseline count - nadir count]).

recovery has not been achieved within 14 days, bone marrow cellularity should be determined. If the bone marrow cellularity is > 50%, no dose adjustments should be made. If bone marrow cellularity is  $\le 50\%$ , treatment should be delayed and the dose reduced according to Table 6-3.

Following dose modifications, the cycle duration should return to 28 days. The reduced dose should be maintained during subsequent cycles that are given unless toxicity develops.

Table 6-3. Azacitidine Dose Modification - Patients With Reduced Baseline Blood Counts

Bone Marrow Cellularity	% Dose in the Next Cycle if Recovery a Is Not Achieved Within 14 Days		
	Recovery a ≤ 21 days	Recoveryª ≥ 21 days	
15-50%	100%	50%	
< 15%	100%	33%	

a. Recovery = counts ≥ nadir count + (0.5 × [baseline count - nadir count])

# **Treatment Interruption and Delays**

If hematological toxicity is observed following azacitidine treatment, the next cycle of therapy should be delayed until the platelet count and the ANC have recovered. If recovery is achieved within 14 days, no dose adjustment is needed. However, if recovery has not been achieved within 14 days, the dose should be reduced according to the azacitidine dose modification guidelines above. Additionally, azacitidine dosing may be delayed for up to 4 weeks based on an individual patient basis, which must be approved by the Medical Monitor. Following dose modifications, the cycle duration should return to 28 days.

In the event 2 or fewer doses of azacitidine are missed during the 7-day dosing period for the R/R and TN/U cohorts, dosing should continue so that the patient receives the full 7 days of therapy. In the event that 3 or more days are missed during the 7-day

dosing period, the Investigator should contact the Sponsor and a dosing decision should be made on an individual case basis.

For the RBC Transfusion-dependent Low-risk MDS Cohort, in the event that 1 dose of azacitidine is missed during the 5-day dosing period, dosing should continue so that the patient receives the full 5 days of therapy. In the event that 2 or more days are missed during the 5-day dosing period, the Investigator should contact the Sponsor and a dosing decision should be made on an individual case basis.

# 6.2.2. Specific Safety Management Guidelines

# 6.2.2.1. Magrolimab

For all cohorts except the RBC Transfusion-dependent Low-risk Cohort, premedication is required before administration of the first 4 doses of magrolimab with oral acetaminophen 650 to 1000 mg and oral or IV diphenhydramine 25 to 50 mg, or comparable regimen. It is also required in case of reintroduction with re-priming. For the RBC Transfusion-dependent Low-risk Cohort, premedication is required for the first 2 doses of magrolimab and the first 2 doses in case of re-introduction with re-priming. In addition, premedications are to be used to manage infusion-related reactions as described below.

## **Management of Infusion-related Reactions**

Infusion-related reactions are defined by the NCI CTCAE (under the category "General disorders and administration site conditions") as "a disorder characterized by adverse reaction to the infusion of pharmacological or biological substances" (Appendix A). For the purposes of this study, the time frame for infusion-related reaction assessment is the 24-hour period beginning from the start of the infusion. Recommendations for the management of infusion-related reactions are provided below.

- For Grade 1 infusion-related reactions, described as mild transient reaction, infusion interruption is not indicated and intervention not indicated:
  - Remain at bedside and monitor patient until recovery from symptoms.

- For Grade 2 infusion-related reaction, infusion interruption is indicated, but patient responds promptly to symptomatic treatment (e.g., antihistamines, non-steroidal anti-inflammatory drugs, narcotics, corticosteroids, IV fluids); and prophylactic medications are indicated for ≤ 24 hours:
  - Stop the magrolimab infusion, begin an IV infusion of normal saline, and consider treating the patient with diphenhydramine 50 mg IV (or equivalent) and/or 500-750 mg oral acetaminophen.
  - o Remain at bedside and monitor patient until resolution of symptoms.
  - Corticosteroid therapy may also be given at the discretion of the Investigator.
  - If the infusion is interrupted, wait until symptoms resolve, then restart the infusion at 50% of the original infusion rate.
  - If no further complications occur after 1 hour (± 10 minutes), the rate may be increased to 100% of the original infusion rate. Monitor the patient closely.
  - If symptoms recur, stop infusion and disconnect patient from the infusion apparatus. No further magrolimab will be administered at that visit.
  - o Premedications should be considered before any future infusions.
  - The amount of magrolimab infused must be recorded on the electronic Case Report Form (eCRF).
  - Patients who experience a Grade 2 infusion-related reaction during the post-infusion observation period that does not resolve to ≤ Grade 1 during that time should be observed until the AE resolves or stabilizes, with vital sign measurements as medically indicated for the management of the AE.
- For Grade 3 or Grade 4 infusion-related reaction, where:
   Grade 3 is described as prolonged infusion-related reactions (e.g., not rapidly responsive to symptomatic medication and/or brief interruption of infusion), or recurrence of symptoms following initial improvement, or where hospitalization is indicated for other clinical sequelae (e.g., renal impairment, pulmonary infiltrates).
   Grade 4 is described as having life-threatening consequences and where urgent intervention is indicated.
  - Immediately discontinue infusion of magrolimab.

- Begin an IV infusion of normal saline, and consider treating the patient as follows: Administer bronchodilators, epinephrine 0.2 to 1 mg of a 1:1,000 solution for SC administration or 0.1 to 0.25 mg of a 1:10,000 solution injected slowly for IV administration and/or diphenhydramine 50 mg IV with methylprednisolone 100 mg IV (or equivalent), as needed.
- The patient should be monitored until the Investigator is comfortable that the symptoms will not recur.
- Patients who have Grade 4 infusion-related reactions occurring with the first dose
   (priming dose) will be permanently discontinued from study treatment.
- Patients who experience Grade 3 infusion-related reactions must be given premedication prior to subsequent doses. In this setting, premedication with oral acetaminophen (650-1000 mg), oral or IV diphenhydramine (25-50 mg), and IV dexamethasone (4-20 mg), or a comparable regimen, is recommended for the subsequent 2 doses. Continued premedication with corticosteroids beyond these 2 doses may be administered at the discretion of the treating physician.
- Patients who receive premedication (with the regimen above, including corticosteroids) and still experience a Grade 3 or 4 infusion-related reaction will be permanently discontinued from study treatment.
- For anaphylaxis, Investigators should follow their institutional guidelines for treatment.
- All patients with Grade 3 or greater infusion-related reactions will be observed until the AE resolves or stabilizes, with vital sign measurements and additional evaluations as medically indicated for the management of the AEs.

#### **Thromboembolic Events**

Thromboembolic events, including deep vein thromboses and pulmonary embolisms, have been reported in some patients receiving magrolimab, sometimes early in therapy. Available data for magrolimab do not support a clear or consistent relationship between

clinical thromboembolic events and magrolimab use. Patients should be closely monitored for the symptoms of thromboembolic events and treated accordingly.

### Anemia, Blood Crossmatching, and Packed RBC Transfusion Procedures

Magrolimab binds to RBCs and leads to erythrophagocytosis. CD47 is a member of the Rh complex in the RBC's membrane. Therefore, when magrolimab binds to CD47, it is likely to interfere with routine blood bank tests needed in case of transfusion. Notify blood transfusion centers/blood banks of this interference with blood bank testing and inform them that a patient will receive magrolimab.

In clinical studies, anemia is the most common treatment-related AE and is typically manifested as a decline in hemoglobin of about 0.5 g/dL to 1.5 g/dL observed in the first 1 to 2 weeks of treatment. This decrease in hemoglobin level is acceptable in patients with no other significant diseases or medical conditions. However, for patients with significant diseases or medical conditions, such as unstable angina, ischemic heart disease, or uncontrolled diabetes mellitus, complications from treatment-related anemia could be life-threatening or fatal. Significant drops (2 to 3 g/dL or higher) have been observed in early doses.

Patients with a low baseline hemoglobin level, especially those with cardiac history or risk factors, must be monitored closely after initial administrations of magrolimab as preexisting anemia could be exacerbated. Red blood cell transfusions are permitted prior to study treatment to ensure adequate hemoglobin level per the investigator's clinical judgment.

All patients must have documented hemoglobin  $\geq 9$  g/dL within 24 hours prior to each of the first 2 doses of magrolimab infusion during initial treatment. Patients who do not meet these criteria must be transfused and have their hemoglobin rechecked to meet 9 g/dL prior to each of the first 2 doses of magrolimab.

Prior to initiation of magrolimab, ABO/Rh type, antibody screen, DAT, and extended RBC phenotyping (including minor antigens such as CcDEe, Cw, MNSs, Kk, FyaFyb, and JkaJkb) will be performed for each patient (Section 7.3.4). Red blood cell

genotyping instead of extended RBC phenotyping is acceptable for any patient. Red blood cell genotyping (instead of an extended RBC phenotyping) must be performed if a patient received any RBC or whole blood transfusion within the previous 3 months (unless laboratory has availability for special techniques for performing phenotyping for patients with recent transfusion). Results must be available before the first dose of magrolimab.

Hemoglobin must be checked again 3 to 6 hours after the initiation of the first and second doses of magrolimab during initial treatment. The patient should be transfused as clinically appropriate. Investigators should consider additional hemoglobin monitoring during the first week of treatment in patients with symptoms of anemia or at increased risk for complications of anemia.

## For Patients After Exposure to Magrolimab:

For all elective RBC and platelet transfusions, use leukocyte-reduced and gammairradiated units per institutional guidelines. For RBCs, phenotype/genotype matched units are preferred. However, CMV-seronegative units for CMV-seronegative patients will not be required for this study.

For instances where the ABO/Rh type cannot be resolved, use pretreatment (historical) phenotype/genotype matched units for minor RBC antigens (CcDEe and Kk, to the extent feasible). Regarding the ABO type, historical blood group or O type can be used as per the institutional guidelines.

For emergency transfusions, the transfusion centers may consider using emergency Group O RBCs if phenotype/genotype matched units are not available.

Whenever possible, blood plasma therapy should be blood type specific. Platelets should be blood type compatible whenever possible and, if not, should have been tested and found not to have high titer anti-A or anti-B. Otherwise, plasma and platelet products can be provided as per the institutional policy.

A recent report has suggested that crossmatch interference by RBCs due to treatment with magrolimab may be resolved by use of gamma-clone anti-IgG and multiple alloadsorptions with papain-treated RBC sample cells, pooled single donor apheresis platelets, or commercial human platelet concentrate product if required (Velliquette 2019) (Troughton 2018).

### **Tumor Lysis Syndrome**

In the case of evidence for tumor lysis syndrome associated with magrolimab and/or azacitidine, patients will be admitted to the hospital as clinically indicated. Standard management will include vigorous IV hydration; correction of acidosis, if present; hypouricemic agents; and close monitoring of serum uric acid, phosphorus, and electrolytes in accordance with local institutional guidelines.

#### 6.2.2.2. Azacitidine

Safety management guidelines for azacitidine are described in Section 6.2.1.2. Additional safety guidelines are provided in the azacitidine prescribing information.

# 6.3. Duration of Therapy

Study treatment (magrolimab and/or azacitidine) will be administered continuously until disease progression, loss of clinical benefit, or unacceptable toxicity. It should be noted that treatment with azacitidine as monotherapy is recommended for a minimum of 6 cycles. All patients in the TN/U Cohort without evidence of treatment failure, relapse after CR/CRi, or unacceptable toxicity should continue study treatment for at least 6 cycles. Patients may be discontinued from the treatment per Investigator's discretion prior to reaching the recommended minimum cycles for any of these reasons detailed in Section 8.1.

### 6.4. Patient Completion of the Study

Patients are expected to remain on study treatment until at least completion of Cycle 6. Patients who have not demonstrated disease progression or unacceptable toxicity may continue to receive study treatment beyond 6 cycles.

Patients are considered to have completed the study treatment period when they finish the Safety Follow-up Visit 30 days (± 7 days) after their last dose of study treatment, unless they are experiencing ongoing serious adverse events (SAEs) or treatment-related AEs. For patients being followed for ongoing SAEs or treatment-related AEs, follow-up visits will continue at least Q4W until resolution to baseline or stabilization of these events, unless the patient starts another anti-cancer treatment. Follow-up for ongoing SAEs or treatment-related AEs after the Safety Follow-up Visit will stop if a patient begins another anti-cancer therapy.

After the Safety Follow-up Visit, patients will enter long-term follow-up for disease progression (Section 7.6) and survival follow-up (Section 7.7).

All patients, including those who discontinue study treatment early, will be followed for response until disease progression or initiation of new anti-cancer therapy, whichever happens first, and followed for survival until death or 3 years after the date of enrollment of the last patient, whichever happens first. For patients who come off study treatment to receive a bone marrow transplant, follow-up for disease progression and collection of SOC bone marrow biopsy/aspirate results will continue until documented disease progression occurs. For any patient who dies during this period, the cause of death must be reported to the Sponsor. All patients must also be followed through completion of all study treatment.

Patients are considered to have completed study participation altogether when they are no longer followed for disease progression or survival (refer to Section 8 for additional details about study discontinuation).

# 6.5. Concomitant Therapy

Anti-leukemic therapies including chemotherapy (with the exception of hydroxyurea or oral etoposide), targeted therapies and immunotherapy are not permitted while patients are on study treatment. Localized non-CNS radiotherapy, erythroid and/or myeloid growth factors, hormonal therapy with LHRH agonists for prostate cancer, and treatment with bisphosphonates RANKL inhibitors are permitted.

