# 2.2. Study Endpoints

# 2.2.1. Primary Endpoints

The primary endpoints for this study are:

[figure not shown]
- Measurement of AEs according to National Cancer Institute Common Terminology
  Criteria for Adverse Events (NCI CTCAE) Version 4.03 or customized AE severity
  grading as defined in the protocol (Appendix A)
- CR rate for patients with AML as defined by the Investigator according to
  protocol-specified criteria (Appendix B), which are based on European Leukemia Net
  (ELN) AML recommendations (Döhner 2017), CR rate for patients with MDS as
  defined by the IWG 2006 MDS response criteria (Cheson 2006)

 8-week RBC transfusion independence rate for patients with low-risk MDS as defined by the lack of RBC transfusions for at least an 8-week consecutive period at any time after starting therapy

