# b. All TN/U Cohorts (meets i or ii):

- Previously untreated patients with MDS defined according to WHO classification, with an IPSS-R (Greenberg 2012) risk category of intermediate, high, or very high risk. Prior and concurrent therapy with hydroxyurea, oral etoposide, erythroid, and/or myeloid growth factors is allowed.
- ii. Previously untreated patients with histological confirmation of AML by WHO criteria who are ineligible for treatment with a standard cytarabine and anthracycline induction regimen due to co-morbidity, age or other factors, or who refuse such therapy.
- c. TP53 Mutant AML Subcohort: Previously untreated patients with histological confirmation of AML by WHO criteria who are ineligible for treatment with a standard cytarabine and anthracycline induction regimen due to co-morbidity, age, or other factors, or who refuse such therapy and who have presence of at least 1 TP53 gene mutation by next-generation sequencing based on local evaluation.

- d. RBC Transfusion-dependent Low-risk MDS Cohort: MDS patients with very low or low risk by IPSS-R who are RBC transfusion-dependent (requiring ≥ 2 RBC units within 8 weeks prior to screening) and meet at least one of the following:
  - Relapsed/refractory to ESA: documented non-response or response that is no longer maintained to prior ESA-containing regimen
  - ii. Intolerant to ESA: documentation of discontinuation of prior ESA-containing regimen at any time after initiation due to intolerance or adverse event
  - iii. ESA ineligible: endogenous serum erythropoietin level > 500 U/L for patients who have not been previously treated with ESAs
  - iv. Have a deletion in chromosome 5q and who are relapsed/refractory/intolerant to or ineligible for lenalidomide therapy
- e. Rollover Cohort: Patients on active magrolimab therapy on the Phase 1 AML (SCI-CD47-002) trial who are deriving clinical benefit by Investigator assessment.
- 2. WBC count ≤ 20 × 10³/mcL pre-first dose of study treatment and prior to each magrolimab dose for Cycle 1. Patients with WBC > 20 × 10³/mcL can be treated with hydroxyurea (up to 4 g/day) throughout the trial to reduce the WBC to ≤ 20 × 10³/mcL. Oral etoposide (up to 200 mg orally [PO] /day) may be given as an alternative to hydroxyurea for patients who are intolerant to hydroxyurea or cannot achieve sufficient WBC lowering on hydroxyurea.
- 3. Patient has provided informed consent.

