## 4.1.2. Exclusion Criteria

- 1. Prior treatment with CD47 or SIRPα-targeting agents (with exception of magrolimab for patients in the Rollover Cohort).
- 2. Prior anti-leukemic therapies including, but not limited to, chemotherapy (with the exception of hydroxyurea or oral etoposide), targeted therapies, immunotherapy, or radiotherapy within 4 weeks prior to Day 1 magrolimab dosing. NOTE: Localized non-central nervous system (non-CNS) radiotherapy, previous hormonal therapy with luteinizing hormone-releasing hormone (LHRH) agonists for prostate cancer, and treatment with bisphosphonates and receptor activator of nuclear factor kappa-B ligand (RANKL) inhibitors are not criteria for exclusion.
- 3. **TN/U Cohorts only**: Any prior anti-leukemic therapy (excluding hydroxyurea or oral etoposide), prior treatment with hypomethylating agents and/or low dose cytarabine.
- R/R Expansion Cohort, R/R MDS Magrolimab Monotherapy Cohort, TN/U
   Cohorts, and RBC Transfusion-dependent Low-risk MDS Cohort only:
   Contraindications to azacitidine, including advanced malignant hepatic tumors or known hypersensitivity to azacitidine or mannitol.
- 5. Acute promyelocytic leukemia.
- 6. Known inherited or acquired bleeding disorders.
- 7. Previous allogeneic hematopoietic stem cell transplant within 6 months prior to enrollment, active graft versus host disease (GVHD), or requiring transplant-related immunosuppression.
- 8. Clinical suspicion of active CNS involvement by leukemia.
- 9. Significant medical diseases or conditions, as assessed by the Investigators and Sponsor, that would substantially increase the risk-benefit ratio of participating in the study. This includes, but is not limited to, acute myocardial infarction within the last 6 months, unstable angina, uncontrolled diabetes mellitus, significant active infections, and congestive heart failure New York Heart Association (NYHA) Class III-IV.
- 10. Second malignancy, except treated basal cell or localized squamous skin carcinomas, localized prostate cancer, or other malignancies for which patients are not on active anti-cancer therapy as defined in Exclusion Criterion 2.

- 11. History of psychiatric illness or substance abuse likely to interfere with the ability to comply with protocol requirements or give informed consent.
- 12. Pregnancy or active breastfeeding.
- 13. Known active or chronic hepatitis B or C infection or human immunodeficiency virus (HIV).

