### 11.8.1.2. Secondary Efficacy Endpoints

Additional parameters of objective response, including CRh, will be evaluated in a similar manner as the primary efficacy endpoints. For the time-to-event endpoints listed here, the Kaplan-Meier (KM) estimates and corresponding 95% intervals for the median will be provided when appropriate. The KM plots may also be provided when appropriate. RBC transfusion independence is defined as no transfusions for at least an 8-week consecutive period. The percent of patients who become RBC transfusion-independent will be estimated based on the number of patients who received at least 1 dose of HuF59-G4 and are RBC transfusion-dependent at baseline.

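### Low-risk MDS cohort: ESAs may be started or increased during treatment, yet the transfusion-independence endpoints ignore them, so an ESA-supported interval counts as response to study treatment

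*Protocol*

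**What the plan says.** **Concomitant treatment.** Section 6.5 names the treatments allowed while patients are on study drug, including "Localized non-CNS radiotherapy, erythroid and/or myeloid growth factors, hormonal therapy with LHRH agonists for prostate cancer". No cohort is excepted, and no dose, timing, stable-dose or washout condition is attached. The washout in Section 4.1.2, exclusion criterion 2, concerns prior anti-leukemic treatment, such as "targeted therapies, immunotherapy, or radiotherapy within 4 weeks prior to Day 1 magrolimab dosing", and does not name erythroid growth factors.

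**Endpoint.** Section 2.2.1 defines the low-risk primary efficacy endpoint as "lack of RBC transfusions for at least an 8-week consecutive period at any time after starting therapy". Section 11.8.1.2 repeats it: "RBC transfusion independence is defined as no transfusions for at least an 8-week consecutive period". Section 2.2.2 adds a 12-week rate and the mean hemoglobin increase. None of these mentions ESA use.

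**Entry.** Under Section 4.1.1, criterion 1d, patients must be RBC transfusion-dependent and "meet at least one of the following". The routes are (i) non-response or lost response to an ESA, (ii) ESA intolerance, (iii) ESA ineligibility, meaning "endogenous serum erythropoietin level > 500 U/L for patients who have not been previously treated with ESAs", and (iv) "Have a deletion in chromosome 5q and who are relapsed/refractory/intolerant to or ineligible for lenalidomide therapy".

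**Data and purpose.** Section 7.3.10 records the name, dose and start and stop dates of concomitant drugs. The synopsis sample size section says the 20 patients are enrolled to look for a first indication of efficacy. It gives no null rate, alpha or power for this cohort.

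**The concern.** In transfusion-dependent low-risk MDS an ESA acts on the very quantity being measured. The protocol allows one to be started or increased on study and then counts any 8-week interval without RBC transfusion, whatever produced it. The cohort has no control arm in which ESA use would appear equally, so the effect of permitted supportive treatment passes straight into the primary rate, and in one direction only. The 12-week rate has the same defect, and the mean hemoglobin increase is exposed in the same way.

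At stake is what the reported rate means as evidence of activity for magrolimab with or without azacitidine. Section 10 and Appendix B already ask, for MDS response, that the impact of anemia be disease-related and not caused by study treatment. Nothing in the protocol guards the opposite direction, where an improvement caused by another drug is credited to study treatment.

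**Working it through.** The protocol states no figure on this point that could be reproduced. The check is a comparison of texts, followed by an illustration of size.

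**1. Does any rule stop an ESA-supported interval from counting?**

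| Place | Limits ESA use, or its effect on the endpoint? |
|---|---|
| 6.5 permitted treatments | No; permitted without condition |
| 4.1.2 exclusion 2 (washout) | No; ESAs not named |
| 2.2.1, 2.2.2 and 11.8.1.2 endpoints | No; ESA use not mentioned |
| 7.3.10 concomitant medication | No; recording only |

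**2. Does eligibility leave only patients in whom an ESA has already failed?**

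| Route (4.1.1, 1d) | ESA non-response or lost response required? |
|---|---|
| i. Relapsed/refractory to ESA | Yes |
| ii. ESA-intolerant | No |
| iii. ESA-naive, erythropoietin > 500 U/L | No, though labelled ESA-ineligible |
| iv. del(5q), by lenalidomide history | No; ESA history not mentioned |

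One route is enough. The exposure therefore lies mainly in routes ii and iv, less in iii and least in i.

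**3. Size per patient.** With about 20 patients (Section 11.4), one misattributed responder adds 1/20 = 5 percentage points.

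**4. Sampling uncertainty for comparison.** Exact (Clopper-Pearson) 95% intervals:
- 4/20 = 20%: 5.7% to 43.7%
- 6/20 = 30%: 11.9% to 54.3%
- 7/20 = 35%: 15.4% to 59.2%

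**5. Illustration with assumed inputs.** Let q be the rate due to study treatment, f the share of patients given a new or increased ESA, and e the chance that the ESA alone produces an 8-week interval. Treating the two effects as independent:

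observed rate = q + (1 − q) × f × e; extra responders = 20 × (1 − q) × f × e

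None of q, f or e is in the protocol. With q = 20%:
- f = 10%, e = 20%: 0.20 + 0.80 × 0.10 × 0.20 = 21.6%, or 0.32 extra responders
- f = 25%, e = 40%: 0.20 + 0.80 × 0.25 × 0.40 = 28.0%, or 1.6 extra
- f = 50%, e = 40%: 0.20 + 0.80 × 0.50 × 0.40 = 36.0%, or 3.2 extra

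Varying q from 10% to 30%, with f from 10% to 50% and e from 20% to 40%, gives 0.28 to 3.6 extra responders.

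Section 1.1 puts transfusion independence after ESA or lenalidomide failure at under one third. The first count above that is 7/20, since 20/3 = 6.7. The chance of 7 or more is 8.7% at a true 20%, 31.7% at 28% and 62.0% at 36%.

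**The case against.** **The SAP may deal with it.** Handling a concomitant drug when deriving a response is often SAP content. Section 11.8 refers analysis details there, and the SAP is not at hand. It may hold such a rule. But the protocol does not leave the endpoint open: it gives a complete definition, which as written counts the ESA-supported interval.

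**The exposed group may be small.** Route i patients have already failed an ESA, and route iii patients are labelled ineligible for one. The numbers entering by routes ii and iv are not given, and nothing shows that any patient started an ESA. This stands; the bias could be close to nil.

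**The cohort is closed.** The title of Table 7-3 says so, and under Section 3.4.1 the step from 6 to 14 further patients rested on safety and efficacy in the first six. This also stands. What remains is the rate to be reported.

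**A stronger reading: the protocol itself calls ESAs standard of care for the del(5q) patients of route iv.** A reader might infer this from Section 1.1. That sentence concerns the untreated lower-risk setting and ties del(5q) to lenalidomide. Section 1.5 says that no standard of care exists for transfusion-dependent low-risk patients who fail ESAs or lenalidomide. The text supports only that route iv does not require ESA failure.

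**A second stronger reading: correcting for ESAs would isolate magrolimab.** It would not. Azacitidine may be added from Cycle 3 in the safety run-in and may be given throughout in the expansion (Table 3-3).

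**Conclusion.** The point holds in a limited form. As written, the protocol credits to study treatment a transfusion-free interval that occurs under a newly started or increased ESA, and only one of the four entry routes makes such an ESA effect unlikely.

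The size is 5 percentage points per affected patient at n = 20. The number affected is unknown, and the 0.28 to 3.6 extra responders above rest wholly on assumed inputs. One such patient is a small shift beside the width of the exact interval, but it can only inflate the rate.

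A reader might infer a false-positive test result or a wrong enrollment decision. The documents support neither: this cohort has no formal test and enrollment is closed. What is affected is the interpretation of a descriptive single-arm rate. The definition should be amended because the correction is cheap and the needed data are already collected.

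**What to change.** In Sections 2.2.1 and 11.8.1.2, and for the 12-week rate in 2.2.2, add for the low-risk cohort: an 8-week or 12-week interval counts towards transfusion independence only if no ESA that was started or increased on study was being given during the interval or within a prespecified carry-over period before it.

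- The sponsor should fix the carry-over period before the rates are derived. The protocol gives no basis for a value. Without a limit, a short early ESA course would bar every later interval, which would be a bias the other way.
- List separately the patients who are independent only with such ESA use.
- Report the rates with and without the rule. The definition would change after enrollment closed, so both figures should be visible.
- For mean hemoglobin increase, keep the planned summary and add a sensitivity summary that leaves out values taken during such ESA use and the same carry-over period.

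The cost is one sentence of definition, one listing and the added summaries, using drug names, doses and dates already collected under Section 7.3.10. Section 6.5 and permitted care stay as they are. The downside is that the primary rate can only stay the same or fall.
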